13.2.3. Recording Adverse Events

Investigators will monitor all subjects for AEs during the trial and establish a diagnosis for an event based on signs, symptoms, and/or other clinical information. It is important to distinguish that individual signs and symptoms of the event are not adverse events and should not be reported.

For each AE, the Investigator will evaluate the causality and severity, report the action taken and event outcome and disclose whether or not it caused the subject to discontinue trial participation.

The following severity scale will be used as a guideline to differentiate the severity of adverse events:

- **Mild (Grade 1)**: Transient or mild discomfort; no limitation in activity; no medical intervention/therapy required
- **Moderate (Grade 2)**: Mild to moderate limitation in activity – some assistance may be needed; no or minimal medical intervention/therapy required
- **Severe (Grade 3)**: Marked limitation in activity, some assistance usually required; medical intervention/therapy required and often requiring hospitalization or prolongation of hospitalization

- **Life-Threatening or Disabling (Grade 4):** Extreme limitation in activity, significant assistance required; significant medical intervention/therapy required; hospitalization, prolongation of hospitalization, or hospice care
- **Fatal (Grade 5)**

An AE that is assessed as severe should not be confused with an SAE. Severity is a category utilized for rating the intensity of an event. An event is described as “serious” when it meets one of the pre-defined outcomes noted in Section 13.2.1.2. Both an AE and SAE can be assessed as severe. However, an AE of severe intensity may not meet SAE definition requirements.

13.2.4. Reporting Adverse Events

All adverse events are collected from the time of signing informed consent for trial participation until completion of 12 months or early termination, whichever occurs first. All AEs occurring after the initiation of the IV catheter placement for the initial dose of IP will be considered treatment emergent. Any ongoing adverse event that has not been resolved at the time of trial completion or early termination for a subject will be marked as ongoing on the adverse event case report form (CRF).

All AEs will be entered into the electronic data capture (EDC) system by trained site personnel at the investigative site.

Expected and unexpected SAEs must be reported to Capricor and entered into the EDC system within 24 hours of discovery of the event. For events that do not have complete information available at the time of initial report, the investigative site will submit all available information at the time of the submission. All SAE Report Forms must be signed by an Investigator and submitted with available source documentation. All source documentation must be de-identified prior to submission.

Should access to the EDC system be unavailable, SAEs and subsequent follow-up information must be reported to Capricor, or designee, via:

- Email: [REDACTED]
- Fax: [REDACTED]

All SAEs must be reported to the respective IRB in accordance with the investigative site’s policies. Copies of the submission will be collected by Capricor.

All SAEs will be reported to the DSMB at least semi-annually, or more frequently at the discretion of the Medical Monitor.

Capricor will promptly upon discovery, report serious and unexpected adverse events for which there is a reasonable possibility that the investigative therapy (i.e. administration product and/or investigative product) caused the events, to the Food and Drug Administration (FDA) in accordance with 21 CFR 312.32 regulations and ICH E2A guidelines.

For trials conducted under an investigational new drug (IND) application, FDA regulations require reporting of any serious suspected adverse reaction that is unexpected according to the current Investigator’s Brochure. A serious adverse reaction is defined as any adverse event for which there is a reasonable possibility that the drug/biologic caused the AE. For the purposes of IND safety reporting, “reasonable possibility” means there is evidence to suggest a causal relationship

between the drug/biologic and the adverse event. Serious, unexpected suspected adverse reactions (SUSARs) are SAEs that are unexpected and are possibly or probably related to participation in the research. Expedited reporting is required for all SUSARs. Capricor will send an IND Safety Report to the FDA within 7 calendar days of receipt for fatal/life-threatening events, and within 15 calendar days of receipt for non-fatal/non-life-threatening events that qualify for expedited reporting.

13.2.5. Pregnancy Reporting

Should a female be impregnated by a trial subject, investigative sites are required to notify Capricor within 24 hours of learning about the pregnancy. The investigative site will receive the Pregnancy Reporting Form to complete and submit to Capricor, or designee.

All pregnancies will be followed until the pregnancy outcome is known. In addition, pregnancies that are ongoing at the time of trial completion will be followed until the outcome is known. The investigative site is responsible for outcome reporting via the Pregnancy Reporting Form, including spontaneous or voluntary termination, details of birth, and the presence or absence of any birth defects, congenital abnormalities, or maternal and newborn complications.

The pregnancy is not an adverse event for the male subject unless there is a suspicion that the investigational product interfered with the effectiveness of a contraceptive medication.

13.2.6. Adverse Event Follow-up

All AEs are followed by the investigative site until an outcome is known or the subject's participation in the trial concludes at either 12 months or early termination, whichever occurs first.

The investigative site is expected to review all ongoing AEs at each visit. AEs are followed until resolution or until no further changes in the event are expected (i.e., the point at which a subject experiencing an AE is treated successfully and stabilized even though he may continue to experience lingering sequelae that may never resolve), or it is agreed that further follow-up of the event is not warranted (e.g., non-serious, IP unrelated, ongoing at final visit).

For SAEs that were incomplete or ongoing at the time of initial submission, the investigative site is required to submit follow-up SAE Report Forms when event information is available to the research site personnel and/or an outcome is known.

14. STATISTICS

14.1. General Considerations

The objectives of the trial are to evaluate the safety and efficacy of intravenous infusions of CAP-1002 administered in four doses at 3-month intervals in subjects with DMD and impairment of skeletal muscle function. All statistical tests will be two-sided with 0.05 significance levels. The detailed description of the trial statistical methods is provided in the Statistical Analysis Plan (SAP). Any deviations from the SAP will be described and justified in the final Clinical Study Report.

14.2. Sample Size

This trial will be limited to a total of 20 randomized subjects.

14.3. Analysis Population

The following analysis populations will be defined for the trial:

Safety Population: Subjects who received IP. Safety endpoints for subjects will be summarized and analyzed according to the treatment actually received.

Intent-to-Treat (ITT) Population: Subjects who were randomized. Subjects will be summarized and analyzed in the treatment group to which they were randomized.

Modified Intent-to-Treat (mITT) Population: For each efficacy parameter, the mITT population will include subjects in the ITT population who have at least a baseline observation (i.e., mITT populations are parameter-specific). Subjects will be summarized and analyzed in the treatment group to which they were randomized.

Per Protocol Population: Subjects who received IP with no protocol deviations/violations that could significantly impact the completeness, accuracy and/or reliability of the trial data. The list of subjects in the per protocol population will be compiled prior to database lock.

14.4. Safety Analysis

Safety parameters will be listed, summarized and, if applicable, analyzed for the safety population. There are no formal tests of hypotheses associated with the evaluation of safety endpoints.

14.4.1. Safety Endpoints

The incidence of the following events through the 12-month timepoint will be **primary safety endpoints**:

- Acute respiratory decompensation within 2 hours following IP administration
- Hypersensitivity reaction
- All-cause mortality
- Serious adverse events
- Treatment-emergent adverse events related to IP or administration procedure

- Immune sensitization syndrome

The incidence and severity of all AEs will be evaluated as the **secondary safety endpoint**.

Treatment groups will be summarized and compared by the incidence of each event type and by the subject event rate. Safety during the study will be monitored by the independent, unblinded DSMB. See Section 13.2 for more detail on AE data collection and processing.

14.4.2. Adverse Events

Directly observed and spontaneously reported AEs will be recorded from time of signing informed consent (SAEs only) through the end of the trial. AEs will be coded using MedDRA® (Medical Dictionary for Regulatory Activities), in which each reported event is mapped to a Preferred Term (PT) and a System Organ Class (SOC). A treatment-emergent AE (TEAE) will be defined as an AE that was not present prior to the initiation of line placement procedure for the IP infusion or was present but worsened in intensity or frequency. All reported AEs will be listed. Both TEAEs and non-TEAEs will be summarized, overall and by severity and relationship to the IP and IP administration procedure. For each SOC and PT within SOCs, the numbers and percentages of subjects reporting an event as well as the number of events that were reported will be calculated. Deaths, AEs that resulted in trial discontinuation, SAEs, and AEs within 24 hours of IP administration will be listed and summarized separately.

14.4.3. Medications

Prescription, over-the-counter, and alternative medication use will be coded to drug class, preferred drug name, and generic/trade drug name using the World Health Organization drug dictionary (WHO-DD). Medications that were stopped before the start of the IP administration procedure will be considered “pre-treatment.” All other medications will be considered “concomitant.” Medications that were started or ongoing at the time the IP administration procedure was started will be considered “baseline” (a subset of “concomitant”). All reported medications will be listed. Frequencies and percentages of subjects reporting or receiving each medication will be summarized by WHO-DD drug class and preferred name within drug class. Pre-treatment and baseline medications will be summarized separately. Separate listings and summaries will also be done for cardiac medications and for glucocorticoids.

14.4.4. Clinical Laboratory Evaluations

Laboratory evaluations will be listed and summarized by visit within each panel (e.g., chemistry, hematology, etc.). Summary tables will show means of observed values and changes from baseline for observations on a continuous scale and distributions of categorical observations. Shift tables may be produced that show frequencies and percentages of subjects that shift from one out-of-range category at baseline to another out-of-range category at subsequent visits.

14.4.5. Donor-Specific Antibodies

Donor, donor profile, allele, and MFI will be listed by HLA and visit. Subject HLA profiles will be provided in a separate listing.

DSA data will be analyzed in the context of immune sensitization syndrome should there be an occurrence.

14.4.6. Physical Examination

Observed status (e.g., normal, abnormal) and changes from baseline in body system-specific physical examination findings will be summarized by visit within each body system.

14.4.7. 12-Lead ECG, Vital Signs, and Weight

Observed values and changes from baseline will be summarized by visit.

14.5. Efficacy Analysis

The primary efficacy endpoint will be evaluated in the ITT population, with supportive analyses in the mITT and PP populations. Secondary and exploratory efficacy endpoints will be evaluated in the PP population.

14.5.1. Primary Efficacy Endpoint

The primary efficacy endpoint is change from baseline to Month 12 in the mid-level (elbow) dimension of the PUL 1.2. The hypothesis set to be tested is:

$$H_0: \mu_c - \mu_p = 0$$

$$H_a: \mu_c - \mu_p \neq 0$$

where μ_c and μ_p are population mean absolute changes from baseline in CAP-1002- and placebo-treated patients, respectively.

14.5.2. Secondary Efficacy Endpoints

Supportive secondary efficacy endpoints will be change from baseline in:

- Mid-level (elbow) PUL1.2 at Months 3, 6, and 9;
- Regional systolic LV wall thickening at Months 6 and 12

14.5.3. Exploratory Efficacy Endpoints

Exploratory efficacy endpoints will be change from baseline in:

- High-level (shoulder) dimension of the PUL 1.2 at Months 3, 6, 9, and 12;
- High-level (shoulder) dimensions of the PUL 2.0 at Months 3, 6, 9, and 12;
- Mid-level (elbow) dimensions of the PUL 2.0 at Months 3, 6, 9, and 12;
- Distal-level (wrist and hand) dimensions of the PUL 1.2 at Months 3, 6, 9, and 12;
- Distal-level (wrist and hand) dimensions of the PUL 2.0 at Months 3, 6, 9, and 12;
- Grip strength, absolute and percent predicted, at Months 3, 6, 9, and 12;
- Tip-to-tip pinch strength, absolute and percent predicted at Months 3, 6, 9, and 12;
- Key pinch strength, absolute and percent predicted at Months 3, 6, 9, and 12;
- Elbow flexion strength, absolute and percent predicted, at Months 3, 6, 9, and 12;
- DMD UL-PROM at Months 3, 6, 9, and 12;

- PODCI scales (subject and parent) at Months 3, 6, 9, and 12;
- DMD-LMS at Months 3, 6, 9, and 12;
- NSAA at Months 3, 6, 9, and 12;
- 10MWRT at Months 3, 6, 9, and 12;
- Incidence of loss of ambulation (10MWRT > 30 seconds) at Months 3, 6, 9, and 12;
- Pulmonary function tests (absolute and percent predicted [if available]) at Months 3, 6, 9, and 12;
- LV structure and function as assessed by cardiac MRI at Months 6 and 12;
- Biomarkers, which may include osteopontin, IL-1 β , IL-2, IL-6, IL-10, TNF- α , CXCL10, troponin I (cardiac, fast skeletal, slow skeletal), troponin T, CK-MM, CK-MB, creatine kinase (total), creatine phosphate, creatinine, myostatin, and follistatin at Months 3, 6, 9, and 12;
- Resource utilization, including hospitalizations for orthopedic injury or surgery and for pulmonary infections, over the course of the trial.

14.6. Statistical Methods

Comparisons between treatment groups on efficacy endpoints will be done using repeated measures linear models. Other analyses may also be done using appropriate parametric or non-parametric methods, depending on distributions of the data and whether or not model assumptions are met. An algorithm detailing the decision-making process for performing the primary efficacy analysis, in light of features of the data that cannot be known until the data are observed (e.g., outliers), will be detailed in the SAP.

14.6.1. Multiplicity

Trial-wise type 1 error is controlled at the 0.05 level by declaring a primary efficacy endpoint. All other efficacy parameters are either supportive secondary or exploratory endpoints and there will be no adjustment for multiple analyses.

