- Biomarker analysis at Week 6, Month 3, Month 4.5¹, and Months 6, 9, and 12 may include:
 - *Muscle inflammation:* osteopontin
 - *Systemic inflammation:* IL-1 β , IL-2, IL-6, IL-10, TNF- α , and CXCL10
 - *Muscle damage:* troponin I (cardiac, fast skeletal, slow skeletal), troponin T, CK-MM, CK-MB, creatine kinase (total), creatine phosphate, and creatinine
 - *Muscle regeneration:* myostatin and follistatin
 - Additional serum collection reserved for future biomarker analyses (i.e., exploratory biomarkers)

Safety

Safety assessments at Week 4 and Months 3, 6, 9 and 12, unless otherwise indicated, will include the following: vital signs, height, weight, physical examination, 12-lead ECG, adverse events, DSA assessment, and clinical laboratory testing (serum chemistry, hematology, and urinalysis). Adverse events and concomitant medications will also be collected during each 14-day post-infusion safety phone call, or if clinically indicated, an unscheduled in-person visit will be performed at the investigative site with targeted assessments based on presentation of signs and symptoms of subject.

Other

The medical resource utilization pharmacoeconomic analysis will explore all-cause hospitalizations, hospitalizations for orthopedic injury/surgery or pulmonary infections, and antibiotic usage. Billing information will not be collected; rather, standardized, composite or bundled costings of national averages will be used in the analysis.

Statistical Methods:

The statistical test for the primary efficacy endpoint will be two-sided and will be conducted using 0.05 significance levels. The detailed description of the trial statistical methods is provided in the Statistical Analysis Plan (SAP).

Sample Size

The trial will randomize 20 subjects.

¹ Biomarker and exploratory biomarker testing at Week 6 and Month 4.5 will be conducted only for those subjects who are able to travel to the investigative site.

Analysis Populations

The following analysis populations will be defined for the trial:

Safety Population: Subjects who begin an infusion of IP. Safety endpoints for subjects will be summarized and analyzed according to the treatment actually received.

Intent-to-Treat (ITT) Population: Subjects who were randomized. Subjects will be summarized and analyzed in the treatment group to which they were randomized.

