14.6.3. Interim Analysis for Futility

The pre-specified interim analysis was performed. Following the interim analysis, further enrollment in the trial was terminated. No further interim analyses are planned.

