3.3 Interim Analyses

3.3.1 Interim Analysis

The interim analysis was performed [REDACTED]

The objective of the interim analysis was to evaluate demographic data for the Intent-to-Treat (ITT) Population, study drug exposure data for the Safety Population, efficacy data for the ITT Population, Modified Intent-to-Treat (mITT) Population and Per Protocol (PP) Population, and safety and adverse event data for the Safety Population. A summary of all listings and tables that were generated to support the analysis of the interim data are outlined in Section 9.2 (APPENDIX B).

The results of the interim analysis were reviewed by the DSMB. Following the interim analysis, enrollment in the trial was discontinued (Protocol Amendment 5 dated September 27, 2019). Subsequently, three additional interim analyses with updated datasets were performed and are described below.

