4.4 Multiplicity

No multiplicity adjustments will be made to any alpha levels used for statistical testing for efficacy endpoints. P-values < 0.05 at the interim analysis were used as an indication of treatment effect for all efficacy endpoints. P-values for all subsequent analyses performed are considered nominal, without conclusions drawn about statistical significance levels.

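### Protocol 14.6.1 claims trial-wise 5% error control, but the interim was read for efficacy at p<0.05 without alpha adjustment, and SAP 4.4 makes every later p-value, including Month 12, nominal

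*Protocol*

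**What the plan says.** **Protocol.** Section 14.6.1 says: "Trial-wise type 1 error is controlled at the 0.05 level by declaring a primary efficacy endpoint". The synopsis says: "The statistical test for the primary efficacy endpoint will be two-sided and will be conducted using 0.05 significance levels". Section 14.1 says: "All statistical tests will be two-sided with 0.05 significance levels". Section 14.6.3 is headed as an interim analysis for futility and ends: "No further interim analyses are planned".

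**SAP.** Section 4.4 makes three statements:

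- It rules out any correction of the testing level: "No multiplicity adjustments will be made to any alpha levels used for statistical testing for efficacy endpoints".
- It then records how the first interim was read: "P-values < 0.05 at the interim analysis were used as an indication of treatment effect for all efficacy endpoints".
- Finally, it sets the status of everything that came afterwards: "P-values for all subsequent analyses performed are considered nominal, without conclusions drawn about statistical significance levels".

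Section 3.3.1 reports that after the interim "three additional interim analyses with updated datasets were performed". Sections 3.3.2 to 3.3.4 describe each of these as an evaluation of unblinded efficacy data. Section 6.1 still sets out a null and an alternative hypothesis, with the Month 12 contrast as the primary comparison. Section 8, which is for departures from the protocol's statistical methods, covers dropped endpoints, the mITT population and the use of ITT alongside PP. It mentions neither the extra looks nor the changed status of the Month 12 test.

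**The concern.** The reason the protocol gives for 5% control covers only one source of multiplicity. A single primary endpoint tested at an interim and again at Month 12, each at 0.05, has more than a 5% chance of a false positive unless alpha is divided between the looks. A look used only for futility would not raise that chance. SAP 4.4, however, says the interim p-values were read for treatment effect.

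The reporting of the primary result depends on this. A reader of the protocol would take a Month 12 p<0.05 as a controlled 5% test, while a reader of the SAP would take it as nominal. A reader of SAP 4.4 could also rely on an interim p<0.05, although no error control is attached to it. The trial stopped at 20 subjects, against about 80 anticipated (SAP Addendum, section 2). Enrolment ended after the interim, and designated sponsor personnel were then unblinded to assignments and aggregate results (Protocol 9.5).

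**Working it through.** **1. The plan's own figure.** One test at two-sided 0.05 gives 1 − (1 − 0.05) = 0.05. So 14.6.1 holds only if the Month 12 contrast is the single test from which an effect can be inferred.

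**2. The passages side by side.**

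| Point | Protocol | SAP |
|---|---|---|
| Month 12 test | Two-sided 0.05 (synopsis, 14.1); trial-wise control claimed (14.6.1) | After the interim, so nominal (4.4); still posed as a hypothesis test (6.1) |
| Role of the interim | Futility (14.6.3 heading) | p<0.05 read for effect on all efficacy endpoints (4.4) |
| Later looks | None planned (synopsis, 14.6.3) | Three, unblinded, on efficacy (3.3.2–3.3.4) |
| Alpha allocation | None shown | No adjustment (4.4) |

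If Month 12 is a 0.05 test, the interim reading at 0.05 adds error that 14.6.1 does not count. If Month 12 is nominal, 14.6.1 has no confirmatory test to which its claim can apply. It fails on either reading.

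**3. Illustrative size: interim plus Month 12, each at 0.05.** The inputs are α = 0.05 two-sided (Protocol 14.1), critical value 1.96, and no adjustment (SAP 4.4). The information fraction *t* at the interim is an assumption, because its date is redacted. The interim used the twenty treated subjects and the trial was then limited to 20, so *t* depends on how much follow-up had accrued.

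Type I error = 1 − P(|Z₁| < 1.96 and |Z₂| < 1.96), with Z₁ and Z₂ bivariate normal and correlation √*t*.

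| *t* | Correlation | Type I error | Constant per-look level that holds 0.05 |
|---|---|---|---|
| 0.25 | 0.500 | 0.0907 | 0.0270 |
| 0.50 | 0.707 | 0.0831 | 0.0294 |
| 0.75 | 0.866 | 0.0734 | 0.0335 |
| 0.90 | 0.949 | 0.0648 | 0.0383 |

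The ceiling, with uncorrelated looks, is 1 − 0.95² = 0.0975.

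**4. All five analyses at 0.05.** SAP 4.4 does not read them this way; the figure only bounds the problem. Simulation of 2,000,000 null paths with independent increments gives:

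| Assumed information fractions | Type I error |
|---|---|
| 0.2, 0.4, 0.6, 0.8, 1 | 0.142 |
| 0.1, 0.25, 0.45, 0.7, 1 | 0.159 |
| 0.5, 0.65, 0.8, 0.9, 1 | 0.111 |
| 0.7, 0.8, 0.9, 0.95, 1 | 0.093 |
| 0.8, 0.85, 0.9, 0.95, 1 | 0.084 |

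**The case against.** The strongest reply is that the SAP already takes the cautious position. The protocol refers readers to the SAP for detailed methods, and SAP section 4 applies 0.05 unless otherwise stated. SAP 4.4 does state otherwise, and it bars significance conclusions from anything after the interim. On that view only an outdated protocol sentence remains. This lowers the risk of an overclaim at Month 12, but it does not remove the contradiction. SAP 8 says version 3.0 replaces earlier SAP versions, not the protocol, and 14.6.1 remains in the current protocol. Nor does the nominal label cover the interim p-values themselves.

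A second reply is that the error rates describe a procedure the SAP does not follow and a model that cannot be checked. The model takes the interim statistic to be the same Month 12 contrast at partial information. Timing and table lists are redacted, so another visit may have driven the interim reading. It also applies normal theory to a 20-subject mixed model. These limits stand, and they are why the figures are illustrations only. Reading all efficacy endpoints at the interim would add error that is not counted here.

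Third, the statement that no further interims were planned may have been true when written, and SAP 3.3 does disclose the three later looks. That is fair. The gap is that they are not reconciled with the protocol.

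Finally, redacted amendment tables or SAP versions not provided might record an alpha allocation. Nothing in the available text shows one, and SAP 4.4 says that no alpha level is adjusted.

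**Conclusion.** The concern holds. Protocol 14.6.1 is wrong as written, because its stated mechanism does not address repeated looks and SAP 4.4 removes the confirmatory status of the test it is meant to protect. This follows from the text alone and needs no assumption about timing.

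The size does rest on assumptions: the same contrast at both looks, independent increments, normal theory and assumed fractions. With the interim and Month 12 both read at 0.05, type I error is about 8.3% at half information, and 9.1% to 6.5% for fractions from 0.25 to 0.9. A constant level of about 0.029 at each look (0.027 to 0.038 over that range) would have been needed to hold 5%. The five-look figure, about 14% with equal spacing and 8.4% to 15.9% over the spacings tried, applies only if all five analyses were read at 0.05.

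Because this decides how the primary result may be claimed, it should be corrected before results are reported.

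**What to change.** 1. **Protocol 14.6.1.** Replace the control sentence with: *Trial-wise type I error control is not claimed. The Month 12 p-value for the primary endpoint is nominal and is reported with the LS-mean difference and its 95% CI.* Align the 0.05 wording in the synopsis and 14.1.
2. **SAP 4.4.** Keep the record of how the interim p-values were read, and add: *No alpha was allocated to the interim and no error control attached to these p-values; they are also nominal and do not support a claim of treatment effect.* If a document fixed before unblinding does show an allocation, state instead the alpha spent and the alpha left.
3. **SAP section 4 and 6.1.** Cross-refer to 4.4, so that the general 0.05 rule and the Month 12 hypothesis test carry the same nominal label.
4. **SAP 8.** List the three unplanned unblinded efficacy analyses and the departure from Protocol 14.6.1 and 14.6.3.

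The cost is wording only, through a protocol amendment and a SAP revision, with no new data or analyses. The downside is a less favourable inferential claim for the primary endpoint.
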